5.3 Concomitant Medications/Vaccinations (allowed & prohibited)

Medications or vaccinations specifically prohibited in the exclusion criteria are not allowed during the ongoing trial. If there is a clinical indication for one of these or other medications or vaccinations specifically prohibited during the trial, discontinuation from trial therapy or vaccination may be required. The final decision on any supportive therapy or vaccination rests with the investigator and/or the participants' primary physician.

Acceptable Concomitant Medications

All treatments that the investigator considers necessary for a participant's welfare may be administered at the discretion of the investigator in keeping with the community standards of medical care. All concomitant medication will be recorded on the case report form (CRF) including all prescription, over-the-counter (OTC), herbal supplements, and IV medications and fluids. If changes occur during the trial period, documentation of drug dosage, frequency, route, and date may also be included on the CRF.

Treatment with bisphosphonates or denosumab for the prevention of bone disease is permitted. GnRH agonists for the prevention of chemotherapy-associated amenorrhea are permitted.

All concomitant medications received within 28 days before the first dose of trial treatment and 30 days after the last dose of trial treatment should be recorded.

Specifically, the following agents are permitted:

- Antiallergic measures such as corticosteroids and antihistamines
- Antiemetics in accordance with ASCO guidance or local standard of care
- Antidiarrheal therapy in accordance with ASCO guidance or local standard of care
- Aspirin, nonsteroidal anti-inflammatory drugs, and anticoagulants are permissible but should be used with caution. However, they should be stopped appropriately prior to biopsy procedures due to risk of bleeding.

Prohibited Concomitant Medications

Participants are prohibited from receiving the following therapies during the Screening and Treatment Phase (combined olaparib and pembrolizumab therapy):

- Antineoplastic systemic chemotherapy or biological therapy
- Immunotherapy not specified in this protocol
- PARPi not specified in this protocol
- Investigational agents other than pembrolizumab and olaparib

- Radiation therapy

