- Live vaccines within 30 days prior to the first dose of study treatment, while participating in the study, and during the 30-day follow up period. Examples of live vaccines include, but are not limited to, the following: measles, mumps, rubella, varicella/zoster, yellow fever, rabies, BCG, and typhoid vaccine. Seasonal influenza vaccines for injection are generally killed virus vaccines and are allowed; however, intranasal influenza vaccines (eg, FluMist®) are live attenuated vaccines and are not allowed.
- Systemic glucocorticoids for any purpose other than for supportive care in the setting of chemotherapy administration as per local guidelines or modulate symptoms from an event of clinical interest of suspected immunologic etiology. The use of physiologic doses of corticosteroids may be approved after consultation with the Principal Investigator.

Participants who, in the assessment by the investigator, require the use of any of the aforementioned treatments for clinical management should be removed from the study. All treatments that the Investigator considers necessary for a participant's welfare may be administered at the discretion of the Investigator in keeping with the community standards of medical care.

Medications or vaccinations specifically prohibited in the exclusion criteria are not allowed during the ongoing study. If there is a clinical indication for any medication or vaccination specifically prohibited during the study, discontinuation from study therapy or vaccination may be required. The final decision on any supportive therapy or vaccination rests with the investigator and/or the participant's primary physician. However, the decision to continue the participant on study treatment requires the mutual agreement of the Principal Investigator, the treating physician and the participant. There are no prohibited therapies during the Post-Treatment Follow-up Phase.

Rescue Medications & Supportive Care

Pembrolizumab

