Weekly differential blood counts including reticulocytes and peripheral blood smear should be performed. If any blood parameters remain clinically abnormal after 4 weeks of dose interruption, the patient should be referred to hematologist for further investigations. Bone marrow analysis and/or blood cytogenetic analysis should be considered at this stage according to standard hematological practice.

Development of a confirmed myelodysplastic syndrome or other clonal blood disorder should be reported as an SAE and full reports must be provided by the investigator.

Management of non-hematological toxicity

Management of new or worsening pulmonary symptoms

If new or worsening pulmonary symptoms (e.g. dyspnea or cough) or radiological abnormalities occur in the absence of clear diagnosis, an interruption in study treatment dosing is recommended and a diagnostic workup should be performed to exclude pneumonitis. Initial workup should consider the inclusion of a clinical evaluation, high-resolution CT scan, ruling-out infection, pulse oximetry, and other appropriate laboratory workup. Pulmonary consultation is highly recommended. Guidelines for the management of patients with immune-related AEs including pneumonitis are provided above.

Following investigation, if no evidence of abnormality is observed on CT imaging and symptoms resolve, then study treatment can be restarted, if deemed appropriate by the investigator. If significant pulmonary abnormalities are identified, these need to be discussed with the Study Physician.

Management of nausea and vomiting

Events of nausea and vomiting are known to be associated with olaparib treatment. In study D0810C00019 nausea was reported in 71% of the olaparib treated patients and 36% in the placebo treated patients and vomiting was reported in 34% of the olaparib treated patients and 14% in the placebo treated patients. They are generally mild to moderate (CTCAE grade 1 or 2) severity, intermittent and manageable on continued treatment. The first onset generally occurs in the first month of treatment with the incidence of nausea and vomiting not showing an increase over the treatment cycles.

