No routine prophylactic anti-emetic treatment is required at the start of study treatment, although it may be delivered. Patients should receive appropriate anti-emetic treatment at the first onset of nausea or vomiting and as required thereafter, in accordance with local treatment practice guidelines. As per international guidance on antiemetic use in cancer patients (ESMO, NCCN), generally a single agent antiemetic should be considered eg dopamine receptor antagonist, antihistamines, dexamethasone.

Renal Impairment

If subsequent to study entry and while still on study therapy, a patient's estimated CrCl falls below the threshold for study inclusion (≥ 51 ml/min), retesting should be performed promptly.

A dose reduction is recommended for patients who develop moderate renal impairment (calculated creatinine clearance by Cockcroft-Gault equation of between 31 and 50 ml/min) for any reason during the course of the study: the dose of olaparib should be reduced to 200mg BD.

Because the CrCl determination is only an estimate of renal function, in instances where the CrCl falls to between 31 and 50 mL/min, the investigator should use his or her discretion in determining whether a dose change or discontinuation of therapy is warranted.

Olaparib has not been studied in patients with severe renal impairment (creatinine clearance ≤ 30 ml/min) or end-stage renal disease; if patients develop severe impairment or end stage disease it is recommended that olaparib be discontinued.

Hepatic Impairment

If subsequent to study entry and while on study therapy, the patient develops hepatic impairment, the investigator should make every attempt to identify the underlying reason for the impairment.

Olaparib can be administered to patients with mild or moderate hepatic impairment (Child-Pugh Classification A or B) with no dose adjustment. Olaparib has not been studied in patients with severe hepatic impairment and is NOT recommended for use in these patients.

Management of toxicity due to either pembrolizumab or olaparib

Both olaparib and pembrolizumab treatment may be associated with the development of pneumonitis, hepatic impairment, and renal toxicity. For renal dysfunction and hepatic dysfunction follow the dose modification guidelines provided above for both olaparib and pembrolizumab.

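### The olaparib nausea guidance names dexamethasone in a phase where systemic glucocorticoids are prohibited, so the primary-endpoint status of a patient who receives it depends on which passage is followed

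*Combined protocol and SAP*

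**What the plan says.** **Nausea guidance (Section 11.3.1).** Antiemetic treatment is to start at first onset, and "generally a single agent antiemetic should be considered eg dopamine receptor antagonist, antihistamines, dexamethasone". The same subsection reports, from an earlier olaparib study, that "nausea was reported in 71% of the olaparib treated patients", against 36% on placebo. Vomiting was 34% against 14%. It describes these events as mostly grade 1 or 2 and manageable, with first onset usually in the first month.

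**Permitted medication (Section 5.3).** The list includes "Antiemetics in accordance with ASCO guidance or local standard of care" and "Antiallergic measures such as corticosteroids and antihistamines". Neither entry mentions a limit on steroids.

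**Prohibited medication (Section 5.3).** The list opens with "Participants are prohibited from receiving the following therapies during the Screening and Treatment Phase (combined olaparib and pembrolizumab therapy" and contains "Systemic glucocorticoids for any purpose other than for supportive care in the setting of chemotherapy administration as per local guidelines". The same entry also exempts treatment of suspected immune-related events, and says that physiologic doses may be approved after consultation with the Principal Investigator.

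**Consequence (Section 5.3).** Participants who, in the investigator's assessment, "require the use of any of the aforementioned treatments for clinical management should be removed from the study". The next paragraph is softer. Stopping study therapy is only a possibility, supportive-care decisions rest with the investigator or primary physician, and "the decision to continue the participant on study treatment requires the mutual agreement of the Principal Investigator, the treating physician and the participant".

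**Endpoint rules (Section 14.0, Sample size).** A patient enters the primary analysis once the 6-week assessment is done; patients who progress earlier are included as failures. Dropping out between weeks 6 and 12, or having no 12-week imaging or biopsy, counts as failure.

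**The concern.** Two operative parts of the protocol give different instructions for the same drug in the same weeks, and Section 5.3 is not consistent within itself about what follows. Clinicians acting in good faith could handle identical patients in three ways.

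The statistical difficulty is that these three ways lead to three different entries in the primary analysis, through a choice of antiemetic and not through the state of the tumor. The trial is open-label and small, and Section 14.0 does not say how a patient who received a prohibited steroid is classified.

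A lesser issue arises if the patient stays in. Systemic steroid exposure would then fall in the period over which immune-cell, TCR and cGAS-STING changes are studied (Section 11.1), and the exploratory analysis plan has no rule for such samples.

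**Working it through.** **1. Do the two rules cover the same period?** Olaparib is given for 6 to 12 weeks with pembrolizumab. Cytotoxic chemotherapy follows only after olaparib has ended and a 2-week washout has passed (Sections 4.1 and 5.1). The prohibited list names the combined olaparib-pembrolizumab phase. The periods coincide.

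**2. Does an exception apply?**
- Chemotherapy supportive care: no cytotoxic chemotherapy is given in this phase.
- Suspected immune-related event: olaparib nausea is not described as one.
- Physiologic doses after consultation: this needs individual approval, and the nausea guidance does not mention it.

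None clearly covers dexamethasone for olaparib nausea.

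**3. What happens to the patient in the primary analysis?**

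| Text followed | Disposition | Status under Section 14.0 |
|---|---|---|
| Section 11.3.1, or the permitted-antiemetic entry in 5.3 | Stays on study | Scored on the week-12 biopsy |
| Mutual-agreement wording in 5.3 | Continues | Scored on the week-12 biopsy |
| Removal sentence in 5.3, before the 6-week assessment, no progression | Removed | Not evaluable |
| Removal sentence in 5.3, weeks 6 to 12 | Removed | Failure |

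With first onset usually in the first month, the third row is the likelier removal route. Section 12.0 provides for replacement only of patients who leave before their first dose, whereas Section 14.0 speaks of up to 23 evaluable patients.

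**4. The plan's design reproduces.** Stage 1 has 14 patients and stops at 7 or fewer responses; the final rule requires 16 or more of 23.
- P(stop) = Σ b(x; 14, p) for x = 0 to 7. At p = 0.50 this is 0.6047 (stated 0.60).
- P(success) = Σ b(x; 14, p) × P[Bin(9, p) ≥ 16 − x] for x = 8 to 14. At p = 0.50 this is 0.0462 (stated limit 0.05); at p = 0.75 it is 0.8016 (stated 0.80).

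**5. Sensitivity to removals.** The documents give no removal rate, so the fractions here are assumptions.

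(a) A fraction f is removed in weeks 6 to 12, independently of response, and scored as failures. The effective rate is 0.75 × (1 − f).

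| f | Effective rate | Power |
|---|---|---|
| 0 | 0.750 | 0.80 |
| 2% | 0.735 | 0.75 |
| 5% | 0.7125 | 0.67 |
| 10% | 0.675 | 0.51 |
| 15% | 0.6375 | 0.36 |

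(b) A fraction e is removed before week 6, is non-evaluable and is replaced. If removal is independent of response, the rate among evaluable patients is unchanged. In the worst case all removed patients would have been non-responders, and a true 50% rate appears as 0.50 / (1 − e). Type I error then rises from 0.046 to 0.056 (e = 2%), 0.076 (5%) or 0.125 (10%).

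**6. What the cited nausea rates can support.** 0.71 × 23 = 16.3 and 0.34 × 23 = 7.8. If those rates held here, about 16 patients would have nausea and about 8 vomiting. These are patients for whom an antiemetic might be chosen. They are not counts of steroid use or of removals.

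**The case against.** The strongest reply is that the conflict is avoidable and the removal rule is not absolute. Dexamethasone is one of three examples, and the other two classes are not on the prohibited list. The removal sentence applies to a participant who requires a prohibited treatment, and a nauseated patient with alternatives may not. Section 5.3 permits antiemetics and leaves room for judgment and for continuation. This stands as a limit on how often the problem would arise. It does not resolve the conflict, because each softer sentence adds another possible disposition for the same patient.

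A second reply is that the protocol uses the word chemotherapy loosely: Section 9.0 speaks of protocol chemotherapy before study treatment, and the imaging part of Section 14.0 describes the 6- and 12-week scans as following neoadjuvant chemotherapy. The supportive-care exception might therefore be meant to reach olaparib. That is possible, and it is why the exceptions are said here not to cover the case clearly. The wording still has to be settled.

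Some stronger readings go beyond the documents:
- A reader might infer that about 16 of 23 patients are affected. The 71% is a nausea rate, and the events are described as mostly mild to moderate and manageable.
- A reader might infer that one removal after week 6 would reverse the conclusion, since 15 and 16 responses fall on opposite sides of the rule. That is true of any single failure for any cause, and it needs a would-be responder, steroid use and enforced removal in the less likely period.
- A reader might infer that the immune results are invalidated. Those objectives are exploratory and descriptive, and steroids for immune events are allowed anyway, so some exposed samples could occur without this conflict.

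**Conclusion.** The text is wrong as written. Sections 5.3 and 11.3.1 conflict on systemic glucocorticoids in the olaparib-pembrolizumab phase, and Section 5.3 conflicts with itself on what follows. Through Section 14.0, the same patient could be scored on the biopsy, be left out of the evaluable set or be counted as a failure.

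The size is unknown, because no rate of steroid use or of consequent removal is given. The power and type I error figures show only what assumed fractions would do; the type I error figures also assume replacement and the least favorable selection. The stated sample size and error rates are correct and are not in question. The effect on the immune-marker objectives is secondary. The point deserves correction because the conflict can change who is treated, removed or counted, and settling it costs almost nothing.

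**What to change.** 1. The clinical team should reconcile the permitted and prohibited lists and the removal and continuation wording in Section 5.3 with the nausea guidance in Section 11.3.1. No view is taken here on which rule is right.
2. Section 14.0 should then state in advance one primary-endpoint classification for patients who receive systemic steroids in this phase, before and after the 6-week assessment, consistent with the reconciled rule.
3. As an addition, repeat the exploratory paired immune-marker summaries without samples taken after systemic steroid exposure. The concomitant-medication record already exists, but Section 5.3 makes the recording of dates optional when medication changes, so steroid dates should be required.

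The cost is amendment wording, a required date field for steroids and one descriptive summary. The drawback is that this summary will rest on fewer patients.

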12.0 CRITERIA FOR REMOVAL FROM STUDY

Patients will be removed from the study when any of the criteria listed below applies. The reason for removal from the study and the date the patient was removed must be documented in the Clinical Research Database system.

All patients who have received at least one dose of each study treatment will be assessable for safety of the combination therapy. Patients who discontinue the study

before receiving their first dose of the study treatments will not be evaluable for safety assessment and should be replaced. Patients whose treatment is interrupted or permanently discontinued due to an AE or clinically significant laboratory value must be followed until resolution or stabilization of the event. A dose delay >3 weeks from the date of the planned dose may require the patient to be discontinued from the study treatment.

Patients are evaluable if they have completed the 6-week assessment. Radiographic response is assessed at 6 and (for those continuing) 12 weeks. Biopsy-confirmation of disease status at 6 and 12 weeks will be conducted at the time of the 6 and (for those continuing) 12 week assessments. pCR/RCB is assessed at the time of surgery.

Patient may continue on study until one of the following criteria applies:

- Confirmed radiographic disease progression
- Intercurrent illness that prevents further administration of treatment
- Unacceptable adverse experiences
- The participant or participant's legally acceptable representative requests to discontinue study treatment
- Physician decides to withdraw a participant from the study treatment or from the study for a reason not listed here
- The participant has a confirmed positive serum pregnancy test
- The participant is lost to follow-up
- Inability of the participant to comply with the requirement of the protocol for treatment or evaluation.
- End of study, whichever occurs first.

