1.0 PROTOCOL SUMMARY AND/OR SCHEMA

Abbreviated Title	Phase II of Neoadjuvant Olaparib in Combination with Pembrolizumab in Patients with Triple Negative Breast Cancer (TNBC) or Hormone Receptor-positive HER2-negative Breast Cancer And Germline Mutations in DNA Damage Repair Genes
Trial Phase	II
Clinical Indication	Neoadjuvant Breast Cancer/Germline mutations in DNA damage genes
Trial Type	Interventional
Type of control	Historical
Route of administration	Intravenous or oral
Trial Blinding	Unblinded Open-label
Treatment Groups	Single arm study Olaparib 300 mg orally BID Pembrolizumab 400 mg intravenously q6weeks
Number of trial participants	23 patients will be enrolled.
Estimated enrollment period	~24 months
Estimated duration of trial	We estimate the trial will require approximately 32 months from the time the first subject signs the informed consent until the last subject's last study-related phone call or visit.
Duration of Participation	Each subject will participate in the trial from the time he/she signs the Informed Consent Form (ICF) until withdrawing consent, becoming lost-to-follow-up, or end of study.
Estimated average length of treatment per patient	Subjects may be on study for ~6-36 weeks.

Trial Schema

Note: Patients in groups 1 and 2 will continue pembrolizumab every 6 weeks after surgery for up to 1 year total

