4.0 OVERVIEW OF STUDY DESIGN/INTERVENTION

4.1 Design

This trial is designed as a single-arm, open-label, non-randomized study with sample size calculated using the Simon two-stage minimax design. The primary endpoint is pathologically negative MRI-guided biopsy after neoadjuvant combination olaparib-pembrolizumab therapy at 12 weeks. Patients are eligible if they have newly diagnosed cT1c-3N0-3M0 invasive breast cancer, either triple negative according to ASCO/CAP guidelines or hormone receptor positive breast cancer with a germline mutation in BRCA1, BRCA2, PALB2, RAD51C, or RAD51D and have undergone a pre-neoadjuvant chemotherapy MRI.

At baseline, consented patients will undergo a research tumor biopsy and the index tumor volume will be quantified on the standard of care breast MRI. Patients will then receive olaparib and pembrolizumab for 6-12 weeks, followed by SOC chemotherapy +/- pembrolizumab and surgery. Depending on response to study therapy, the sequence of cytotoxic chemotherapy +/- pembrolizumab vs surgery will be determined by the primary clinical team. At the 6-week timepoint, all patients will undergo MRI for tumor assessment of interval response, which will be immediately followed by a concurrent MRI-guided biopsy. Similarly, at the 12-week timepoint, all patients who remain on olaparib/pembrolizumab for > 6 weeks will undergo another MRI for tumor assessment of interval response, which will be immediately followed by a concurrent MRI-guided biopsy.

At 6 weeks of treatment, the first study MRI will be performed, and treatment response will be assessed by comparing difference in tumor volume on this MRI to that measured on the pre-neoadjuvant chemotherapy MRI. Patients will be categorized as follows:

Group 1: Decrease in tumor volume

- 1a) Decrease in tumor volume of at least 50% ($\geq 50\%D$)
- 1b) Decrease in tumor volume of 0 to 50% ($< 50\%D$)

Group 2: Enlargement in tumor volume of 0 to 25% ($< 25\%E$)

Group 3: Enlargement in tumor volume of 25% or greater

All evaluable patients across the 4 categories will be included for the primary endpoint.

Patients who are responding (any decrease in tumor size, groups 1a and 1b above) will continue the study therapy for 6 additional weeks after the initial tumor

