At 6 weeks patients will be categorized as follows: 1a) Decrease in tumor size at 6-weeks of at least 50% ($\geq 50\%D$) 1b) Decrease in tumor size at 6-weeks of 0 to 50% ($< 50\%D$) 2) Enlargement in tumor size of 0 to 25% ($< 25\%E$) 3) Enlargement in tumor size of 25% or greater at 6 weeks ($> 25\%E$). Patients who clinically progress before the 6 week assessment will be taken off study and undergo SOC treatment. Patients with a decrease in the size of the tumor at the 6-week study assessment will continue olaparib and pembrolizumab for an additional 6 weeks for a total of 12 weeks and then proceed with SoC chemotherapy or definitive surgery, at the discretion of the primary clinical team. Patients with enlargement in tumor size of 0-25% at the 6-week study assessment will either continue olaparib and pembrolizumab for an additional 6 weeks for a total of 12 weeks and then proceed SoC chemotherapy/pembrolizumab and surgery or immediately change to SoC chemotherapy or proceed with definitive surgery at the discretion of the primary clinical team. Patients with > 25% enlargement in tumor size at the 6 week study assessment will proceed with SoC chemotherapy or definitive surgery at the discretion of the primary clinical team. The sequence of cytotoxic chemotherapy vs surgery in the scenarios above will be determined through multidisciplinary coordination of care by the primary clinical team (breast medical oncology/breast surgery/radiation oncology).

BREAST MRI- MRI Guided biopsies:

The MRI-guided biopsies will be performed by investigators from the Breast Radiology Service. The research MRI guided percutaneous biopsy technique will be similar to that performed for clinical diagnosis except intravenous contrast will have already been administered for the preceding breast MRI and will not be given again. All MR guided biopsies will be performed with either a 1.5-T or 3.0T whole-body MRI GE unit equipped with a dedicated 8- or 16-channel surface breast coil. On the day of the procedure, the site of biopsy proven enhancing cancer and/or tumor bed will first be localized with MRI using tumor enhancement, the accurately positioned pre-NAC

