There are several secondary endpoints. First, safety and tolerability of the study regimen will be summarized using frequencies according to the CTCAE Version 5. Common side effects are listed in Section 15.0. The rate of pathologically negative MRI-guided biopsy at 12 weeks will be calculated in the subpopulation of patients with PD-L1-positive disease. In the neoadjuvant setting the rates of PD-L1 positivity were reported in two large prospective trials: Keynote 522 ~80% of patients with TNBC were PD-L1+ and in the NeoTrip trial ~56% of tumors were PD-L1+. In the metastatic setting the numbers have been varied but in the large clinical trials the rate of PD-L1 positivity was ~40%.

Data on MRI-guided biopsies and MRI images will be collected at baseline, at 6 weeks and at 12 weeks following entry into the study. The correlation of response as measured by the MRI - guided biopsy vs MRI images will be evaluated at each timepoint using the McNemar's test for paired samples. The correlation of response as measured by the MRI-guided biopsy collected post-treatment vs pCR at surgery will be evaluated using the McNemar's test for paired samples and the Kappa statistic. The overall pathologic complete response rate will be calculated with a 95% confidence interval.

Analysis of exploratory endpoints

These exploratory analyses will be descriptive/graphical in nature, and are designed to generate new hypotheses to be tested in future clinical studies.

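### Section 12.0 takes patients off study, not only off treatment, and the secondary pCR rate has no denominator or missing-data rule to cover those removed

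*Combined protocol and SAP*

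**What the plan says.** Section 12.0 opens its removal list with "Patients will be removed from the study when any of the criteria listed below applies". Entries include "Confirmed radiographic disease progression", "Unacceptable adverse experiences", intercurrent illness that prevents further treatment, and a participant's request to stop study treatment. The entry on physician decision mentions leaving treatment and leaving the study as separate things, but both fall under the same removal rule. Section 4.2 adds: "Patients who clinically progress before the 6 week assessment will be taken off study and undergo SOC treatment".

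Other parts of the document point the other way:

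- Section 1.0 keeps each subject in the trial "until withdrawing consent, becoming lost-to-follow-up, or end of study".
- Study Calendar footnote c times the discontinuation visit from the last pembrolizumab dose or, for group 3 patients who do not continue the combination, from surgery.
- Section 2.0 defines the secondary pCR objective over the patient population, after combination therapy with or without standard chemotherapy.
- Section 11.0 (Pathologic analysis) takes surgical results retrospectively from the final pathology report.

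On analysis, the Sample size part of Section 14.0 counts as failures those who progress in the first 6 weeks, those who progress or drop out in weeks 6 to 12, those who switch to standard therapy, and those with no week-12 assessment. These rules are written for the primary endpoint. For pCR the plan says only: "The overall pathologic complete response rate will be calculated with a 95% confidence interval".

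**The concern.** Progression, toxicity and a request to stop are reasons to end study treatment. Section 12.0 makes them reasons to end study participation. The pCR objective needs the surgical outcome of exactly these patients, because it covers those who go on to standard chemotherapy before surgery. A site that follows Section 12.0 to the letter may record no surgical outcome for them.

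The primary endpoint has a rule for this situation and pCR has none. If removed patients without a recorded outcome are left out, the pCR rate and its comparison with the week-12 biopsy would describe mainly patients who stayed on the combination. Where removal was for progression, the rate would be too high.

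**Working it through.** **1. The plan's own design figures.** Section 14.0 states a Simon minimax design: 50% versus 75%, stop at 7 or fewer of 14, success at 16 or more of 23. An exact two-stage binomial calculation gives type I error 0.046, power 0.80 and a probability of early stopping under the null of 0.60. These agree with the stated 0.05 (a ceiling), 0.80 and 0.60. The point below does not change them.

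**2. Which rule covers a removed patient?**

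| Question | Primary endpoint | Secondary pCR |
|---|---|---|
| Progression before week 6 | failure (Section 14.0) | off study (Section 4.2); no analysis rule |
| Progression or dropout, weeks 6 to 12 | failure (Section 14.0) | progression removes from study (Section 12.0); no analysis rule |
| Outcome missing | failure (Section 14.0) | no rule |
| Denominator | evaluable patients plus early progressors | not stated |

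**3. Size of the effect on pCR.** The documents give no expected pCR count and no removal rate, so the counts here are assumptions. Let x be the number of pCRs, N = 23 the number treated, and k the number of non-pCR patients who leave the denominator. The reported rate is x/(N − k). Exact 95% intervals are in brackets for x = 12.

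| k | x = 12 | x = 16 |
|---|---|---|
| 0 | 12/23 = 52.2% (30.6 to 73.2) | 16/23 = 69.6% |
| 1 | 12/22 = 54.5% (32.2 to 75.6) | 16/22 = 72.7% |
| 3 | 12/20 = 60.0% (36.1 to 80.9) | 16/20 = 80.0% |
| 5 | 12/18 = 66.7% (41.0 to 86.7) | 16/18 = 88.9% |

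At x = 12 the shift is 60.0 − 52.2 = 7.8 points for k = 3 and 66.7 − 52.2 = 14.5 points for k = 5. For scale, Section 14.0 quotes pCR ranges of about 44–54% (chemotherapy) and 53–65% (immunotherapy or targeted agent). Their midpoints, 49% and 59%, are 10 points apart.

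**4. Direction.** If retained patients have pCR rate p and the k removed patients have rate q, leaving out the removed patients overstates the all-treated rate by (k/N)(p − q). Take k = 4, N = 23, p = 0.60:

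- q = 0: the all-treated rate is (19 × 0.60)/23 = 11.4/23 = 49.6%, an overstatement of 10.4 points.
- q = 0.50: (11.4 + 4 × 0.50)/23 = 13.4/23 = 58.3%, an overstatement of 1.7 points.
- q = 0.60: no bias.

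The bias is upward only if removed patients do worse than retained ones. That is the natural expectation for progressors. It is not established for patients removed for toxicity.

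**5. Week-12 biopsy.** Section 4.1 first says "all patients who remain on olaparib/pembrolizumab for > 6 weeks will undergo another MRI", followed by a biopsy. Later in the same section the requirement is for those who continued for the further 6 weeks. The Study Calendar and Section 12.0 limit it to patients who continue. A patient who stops at, say, week 9 falls under the broader of these statements but arguably not under the others.

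**The case against.** The best defence is that the documents, read as a whole, intend follow-up to surgery. The pCR objective covers the whole population, Section 12.0 itself says pCR is assessed at surgery, footnote c follows group 3 to surgery, and pathology comes from the routine report. Section 14.0 does not say that removed patients leave the denominator. This stands in part: loss of pCR data is a risk, not a stated outcome. It does not remove the contradiction with Section 12.0 or supply the missing rule.

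Five stronger readings are tempting but not supported:

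- *Group 3 patients are all removed as progressors.* Group 3 is defined by at least 25% growth in volume, and Section 13.1 defines progression as at least 20% in longest diameter. For a sphere, 25% in volume is 1.25^(1/3) − 1 = 7.7% in diameter, and 20% in diameter is 1.2³ − 1 = 73% in volume. Section 13.3 is looser, calling any tumour larger than baseline progressive, so the trigger itself is unclear.
- *Section 5.3 removes anyone who needs chemotherapy.* Its sentence that participants who "require the use of any of the aforementioned treatments for clinical management should be removed from the study" belongs to a list confined to screening and the combination phase. The same section prohibits nothing in post-treatment follow-up, and standard chemotherapy is the planned next step.
- *Only the adverse event is followed after removal.* Footnotes c and w and Sections 15.1 and 15.2 also require a discontinuation visit and continued adverse event and SAE reporting.
- *The week-12 biopsy is already mandatory for early stoppers.* Only the broader wording in Section 4.1 suggests this.
- *The trial loses power.* If 5% or 10% of responders lost their biopsy, the response rate would be 0.75 × 0.95 = 0.7125 or 0.75 × 0.90 = 0.675, and power 0.67 or 0.51. Both loss rates are assumed. The calculation also takes the 75% to exclude such failures, which Section 14.0 does not say. If 75% already includes them, power stays at 0.80.

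**Conclusion.** The point holds as a conflict between sections and a gap in the analysis plan for a secondary endpoint; it should be fixed. Sections 12.0 and 4.2 end participation for events after which Sections 1.0 and 2.0 and footnote c still expect the patient to be on study, and nothing in Section 14.0 says how such patients enter the pCR rate.

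The likely bias is upward for progressors and of unknown direction for toxicity removals. In the illustration, 3 to 5 lost non-pCR patients add about 8 to 14 points at 12 pCRs. This rests on assumed counts and on all lost patients being non-pCR. It is smaller than the half-width of the interval for 12/23, (73.2 − 30.6)/2 = 21 points, but that interval does not account for the bias.

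The primary endpoint is protected: counting missing week-12 results as failures cannot inflate type I error. The question left there is one of consistency, namely whether a patient who stops between weeks 6 and 12 is to be biopsied at week 12.

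**What to change.** 1. In Section 12.0, separate discontinuation of study treatment from withdrawal from the study, and align the wording on early progressors in Section 4.2 with that split and with Section 1.0.
2. Collect the routine surgical pathology report for every treated patient who has not withdrawn consent, whatever the reason for stopping.
3. In Section 14.0, define the pCR rate over all treated patients, with no surgery or missing pathology counted as non-pCR. Give the rate among patients who had surgery as a sensitivity analysis.
4. Separately, reconcile the two wordings in Section 4.1 with the Study Calendar and Section 12.0 on whether a patient who stops study therapy between weeks 6 and 12 has the week-12 MRI and biopsy. Which answer is chosen is for the sponsor.

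Items 1 to 3 cost protocol wording and one extra table, since Section 11.0 already relies on the routine report. Sample size, type I error and design power do not change. The downside is a possibly slightly lower reported pCR rate. The all-treated rate is also conservative if some unrecorded outcomes were pCRs: with 12 observed and 3 unknown, the truth lies between 12/23 = 52.2% and 15/23 = 65.2%. This is why collecting the reports matters more than the imputation rule. The cost of item 4 depends on the answer: the broader wording would mean a further contrast MRI and research biopsy in patients who have stopped treatment.
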